Peripheral neuropathy is currently the second most common side effect after chemotherapy, second only to the side effects of blood toxicity. A variety of chemotherapy drugs may induce peripheral neurotoxicity and be caused by the cumulative dose of chemotherapy drugs. Symptoms include sensory paresthesia, feeling dullness or numbness, glove-like feeling distributed in the palm. The currently most effective way is to interrupt the treatment or adjust the dose of chemotherapeutic drugs, but it is easy to make patients discontinue chemotherapy. The purpose of this study is to explore the impact of acupuncture on neurological symptoms and quality of life. Three kinds of questionnaires will be used:(1) Brief pain inventory- short form to assess the extent of pain and the impact of daily life. (2) FACT/GOG-NTX-13 (Version 4) assess changes in neurological symptoms; (3) WHOQOL-BREF to assess changes in patients' quality of life. The course of treatment was evaluated for nine weeks. Changes in neurological function and quality of life will be evaluated before treatment, the third week of treatment, the sixth week of treatment, till the ninth week. The aim of this study is to confirm that acupuncture can improve peripheral neuropathy after chemotherapy in order to enhance breast cancer patients' quality of life and provide a new opportunity for integrative therapy between Chinese and Western medicine.

C. Background and purpose of the research

Please describe in detail the background, purpose, and importance of this research plan, as well as domestic and international research on this plan and important references

(i) Background of the research

A variety of neurotoxic chemotherapeutic agents, including platinums (e.g. cisplatin, carboplatin, and oxaliplatin), taxanes (e.g. paclitaxel and docetaxel), and vinca alkaloids (e.g. vincristine and vinblastine), thalidomide and bortezomib, may induce peripheral neuropathy. Generally speaking, sensory nerve dysfunction is more common than motor involvement. It causes hands and feet to feel tingling, dullness or numbness symmetrically, a glove-like ("glove-and-stockings type") sensation distributed in palms and soles. Patient's touch, vibration, and proprioception senses may be impaired under clinical examinations[1].

CIPN relates to the cumulative doses of chemotherapeutic agents. Sometimes, when chemotherapy is stopped, neuropathy symptoms may continue or worsen, which is called a "costing phenomenon." Nerve damaging usually starts from the ends of the extremities; while individual doses were accumulated, it gradually extends to proximal joints or ganglions. CIPN is currently the second most common side, next to hematotoxicity. Within thirty days after chemotherapy, 68.1% of patients may develop CIPN, most of which can be relieved or improved, but there are still 30-83% symptoms persist over 6 months[1].

At present, the most effective way to treat CIPN is to stop the treatment protocol or adjust doses of chemotherapy; however, it affects the effect of chemotherapy in degrading tumor growth. Plenty of pharmacological or non-pharmacological treatments are still under investigation, such as antioxidant medication (e.g. Acetyl-L-carnitine, glutamine, vit B₁₂, fish oil, etc.), anxiolytics (e.g. venlafaxine), neuroprotective agents (e.g. infusion of calcium ions, magnesium ions), food supplements, acupuncture, light stimulation, etc. Acupuncture with the advantages of clinically effective, easy-practice and relatively safe, few studies revealed its effect on CIPN. However, there is still a lack of large clinical trials to evaluate its effectiveness[1].

(ii) Purpose of the research

To investigate the efficacy of acupuncture on peripheral neuropathy after chemotherapy administration in patients with breast cancer.

(iii) Importance of the research

Current studies revealed that acupuncture might be useful on CIPN; however, an insufficient number of participants or lack of control groups limit the quality of clinical studies. Therefore, the aim of our study to conduct a randomized controlled clinical trial to evaluate the efficacy of acupuncture on peripheral neuropathy caused by chemotherapy.

(iv) Domestic and international researches on this plan

In 2013, Giovanna Franconi et al. published a systematic review that screened the database of MEDLINE, Google Scholar, Cochrane Database, CINHAL, CNKI, Wanfang Med Online, ISI Proceedings. The screened year was set before 2012, and 3989 journal articles were screened. With excluding acupuncture irrelevant or duplicate articles, or researches unrelated to neuropathy and

chemotherapy, 98 papers left for quality evaluation, and 7 articles were selected finally which most relevant to the effect of acupuncture in treating CIPN. As the results of the two randomized controlled-trials selected in the seven articles, a prospective randomized controlled clinical trial conducted by Alimi et al. in 2003, auricular acupuncture for 2 months was significant improved in visual analog scale(VAS) compared with a controlled group(placebo acupuncture and seeds); another randomized controlled trial conducted by Tian et al. in 2011, warm acupuncture and moxibustion without knowing treatment duration, the quality of life and neurotoxic symptoms were improved compared with neurotropin [2].

Raimond et al conducted a phase II clinical trial in 2016, acupuncture-like transcutaneous nerve stimulation (ALTENS) was used in the experimental group, and the acupoints were patched on the seventh cervical vertebra in combination with Hegu, and the third Lumbar spine in combination with Tai-Chong. The protocol included 12 treatments, and 20 minutes remained in each treatment; all participants were followed up for 3 and 6 months from the end of treatments. Of 27 patients in ALTENS group, 24 completed the 3-month follow-up after treatment, and 23 completed the 6-month follow-up. Compared with the real acupuncture group, only 13 people were included. Although the results after acupuncture are listed, there were insufficient data to assess the differences between the two groups. Although studies have shown that ALTENS relieved symptoms of neurotoxicity using Modified total neuropathy score (mTNS), numbness score and Edmonton Symptom Assessment Scale (ESAS), there lacked a control group and randomized sampling design in this study[3].

This randomized controlled clinical trial explores the efficacy of combined acupuncture and drug treatment (conventional cancer therapy) in women with breast cancer after chemotherapy causes peripheral neuropathy. The study adopted convenience sampling and randomized allocation, all the participants were screened from the patients with breast cancer who visited the Department of Traditional Chinese Medicine at Tainan Municipal An-Nan Hospital-China Medical University, Tainan, Taiwan.

The inclusion criteria will be: female more than 20 years of age; breast cancer with early-stage at I-III; had completed chemotherapy; the neurotoxic chemotherapeutic agents included taxanes, platinums, or others; less than grade three in the Eastern Cooperative Oncology Group (ECOG) status; higher than grade one in National Cancer Institute-common terminology criteria for adverse events(NCI-CTCAE) scale.

The exclusion criteria will be: having less than three months in mean survival time, history of diabetic neuropathy before chemotherapy administration, history of other preexisting peripheral neuropathy, other inflammatory or metabolic arthritis, severe blood coagulation diseases or with latent bleeding tendency, unstable cardiovascular diseases, or other preexisting muscle-skeletal diseases.

Figure 1 showed the flow chart of the research:

[figure not shown]

Figure 1. The flow chart of the study

The evaluation tools used in the research are:

- (1) Brief Pain Inventory-short form: To assess the location of pain and the level of pain. Items are scored from 0 to 10 (0= no pain; 10= pain as bad as you can imagine) to evaluate the degree of pain and the impact of pain on daily life.
- (2) FACT/GOG-NTX-13: To evaluate the changes in peripheral neuropathy such as sensory, motor, touch, cold and heat sensations, and the impact of pain on daily life. Items are scored from 0-4 (0 = not at all; 4 = very much) and summed.
- (3) WHOQOL-BREF (Taiwan version): To evaluate the degree of improvement in the quality of life after receiving acupuncture treatment. Items are scored from 1-5 (1 =being very dissatisfied, 2 =dissatisfied, 3 =No comments, 4 =satisfaction, 5 =very satisfied).
- (4) Touch Test Sensory Evaluator: Use 20 von Frey monofilaments to test the degree of the tactile sensation of the patient's fingertips, tips of the toe, palms, and planters.

The treatment protocol will be designed as:

- (1) The acupuncture group: Acupuncture treatment will be performed for 9 weeks. The frequency of acupuncture will be twice a week for the first six weeks, and once a week for the following three weeks. 30 minutes needling at each treatment. Acupuncture points include Baihui(GV20), Qihai(CV6), Quchi(LI11), Hegu(LI4), Neiguan(P6), or Shenmen(HT7) for upper limbs. For plantar numbness, choose two acupoints to use in turn; use Weizhong(BL40), Sanyinjiao(SP6), or Zusanli(ST36) for lower limbs. If severe numbness occurred, Taixi(KI3) or Yongquan(K1) should be added for feet numbness. “De qi” sensation, such as soreness, numbness, pain, etc. will be achieved at each acupoints .

(2) The controlled group: Acupuncture with minimal needling 0.5 *cun* (estimated 1cm with deviation depends on the body size of each participant) away from the acupoints, which only superficially penetrated the skin without the feeling of “De Qi” sensation.

The conventional cancer treatment for CIPN was the same in the two groups.

Within nine weeks of treatments, questionnaires were assessed before treatment, at week three, week six, and week nine to follow-up the changes of peripheral neuropathy on each participant.

Explore the neuroprotective mechanism of acupuncture: 15 cc of blood samples will be drawn before and after 15 sessions of treatments from participants in both groups. The blood samples will be analyzed by enzyme-linked immunosorbent assay (ELISA) for tumor necrosis factor-alfa and interleukin- 6, interleukin-10 and brain-derived nuerotrophic factor to evaluate the differences in the inflammation state of the peripheral nervous system within and between groups.

Statistical analysis:

This is a two-group, parallel controlled clinical trial; the null hypothesis will be no significant difference in BPI-SF between the two groups. The estimated standard deviation was 2, the power was set to 94%, a two-tail test, $\alpha=0.05$, and the estimated number of patients was at least 25 in each group.

A two-sample t-test will be used to compare the difference between the treatment group and the controlled group.

A Paired-t-test will be used to compare the changes in the assessment scale at week 3, week 6 and week 12.

One way ANOVA: Analyze the relationship between the demographic data of subjects, breast cancer grade and other category variables and the evaluation scale.

(ii) Expected difficulties and solutions

The treatment group often withdrew from the trial due to frequently acupuncture or bleeding caused by acupuncture. The solution is to specify the possible side effects of acupuncture, such as bleeding or bruising, in the informed consent form.

The control group may not be able to continue treatment due to low efficacy. The way of solution is to strive for subject allowances.

E. The expected work items and specific results

1. Please list the work items expected to be completed within the implementation period.
2. Expected contributions to academic research, national development and other applications.
3. Expected training for participating staff members.
4. For projects that last more than one year, please list them by year.

(i) Work items expected to be completed within the implementation period

1. To submit the protocol to the Research Ethics Committee of the hospital for ethical review.
2. To establish patients' basic characteristic datasheets.
3. To obtain authorization and preparation of assessment scales
4. To update related articles in journals or books about the study
5. To pre-test and adjust study procedures.
6. To screen eligible participants and complete the assessments
7. documentation of study data.
8. statistical analysis.
9. Prepare an interim report
10. Prepare results reports
11. Send an application for the research funding.

(ii) Expected contributions

Until now, most studies focused on the effect of acupuncture or traditional Chinese formulas in the treatment of CIPN. The aim of this study is to investigate the effect of acupuncture with conventional cancer therapy in the treatment of CIPN, in order to prove the effect of intervention with traditional Chinese medicine in treating cancer treatment-related symptoms.

(iii) Expected training for participating staff members

The staff participating in the research will understand the research ethics, the process of experimental design, the importance of the informed consent form, and the authorization and preparation of evaluation tools. Through data collection and analysis, the staff can learn how to use statistical software, data analysis, and write credible professional medical articles.

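### Time since the last chemotherapy dose is plausibly prognostic but is not used in the readable allocation or arm comparison; using it is a cheap gain in precision, not a repair of validity

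*Combined protocol and SAP*

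**What the plan says.** **Entry.** Section D(i), inclusion criteria, asks that patients "had completed chemotherapy; the neurotoxic chemotherapeutic agents included taxanes, platinums, or others". No inclusion or exclusion criterion sets a shortest or longest interval since the last dose.

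**Natural course.** Section C(i), Background of the research, says: "Sometimes, when chemotherapy is stopped, neuropathy symptoms may continue or worsen". Of cases arising within thirty days after chemotherapy it adds: "most of which can be relieved or improved, but there are still 30-83% symptoms persist over 6 months".

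**Allocation.** Section D(i) says: "The study adopted convenience sampling and randomized allocation". The readable text mentions no blocking, stratification or minimisation. The flow chart, Figure 1, is not shown.

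**Analysis.** Under Statistical analysis in D(i): "A two-sample t-test will be used to compare the difference between the treatment group and the controlled group". No covariate is named. A further analysis is listed: "One way ANOVA: Analyze the relationship between the demographic data of subjects, breast cancer grade and other category variables and the evaluation scale". Time since chemotherapy is not named there.

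**Size.** The hypothesis concerns BPI-SF: "the null hypothesis will be no significant difference in BPI-SF between the two groups". The inputs are: "The estimated standard deviation was 2, the power was set to 94%, a two-tail test", with alpha 0.05 and at least 25 patients per group. The target difference is not stated.

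**The concern.** A patient a week after her last taxane dose and a patient three years after hers are both eligible. On the background's own account, the first may still be worsening or may be about to recover, while the second has symptoms that have persisted. Their expected change over nine weeks without acupuncture therefore plausibly differs.

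In a trial of about 50, the arms can differ by chance in their mix of recent and long-standing cases. An unadjusted comparison carries that difference into the estimated effect, in either direction, and leaves the variation due to timing in the error term. Adjusting for baseline score alone would not fully deal with it, because two patients with the same score may be at different points in their course. The mix also makes a positive result harder to read: it could mean faster recovery of recent neuropathy or relief of persistent neuropathy.

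**Working it through.** **1. The plan's sample size.** Inputs from Statistical analysis: SD 2, power 94%, two-sided alpha 0.05, 25 per group. The target difference is missing, so the 25 cannot be reproduced from the stated inputs alone. Solving for the difference gives 1.99 points (normal approximation) or 2.03 (noncentral t). With an assumed difference of 2.0, n = 25 per group; power is 94.2% (normal) or 93.4% (t). The plan is therefore consistent with a target of about 2 points.

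**2. Noise already in the comparison.** Taking SD 2 as the SD of the quantity compared:
- Standard error = 2 × √(2/25) = 0.57.
- Smallest significant difference = 2.01 × 0.57 = about 1.14 points (t, 48 df).

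**3. Chance imbalance.** Let p be the share of recent cases (assumed; the documents give none). The number in each arm is treated as Binomial(25, p), that is, unrestricted allocation, which is also an assumption.

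| Difference in share between arms | p = 0.5 | p = 0.3 |
|---|---|---|
| at least 20 points (5 patients) | 20.3% | 16.4% |
| at least 24 points (6 patients) | 11.9% | 8.8% |

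The SD of the difference in shares is √(2p(1−p)/25) = 0.141 at p = 0.5.

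**4. Shift in the estimate.** Let g be the gap in untreated BPI-SF change between recent and long-standing cases (assumed 1 to 2 points). Shift = imbalance × g.
- 0.20 × 1 = 0.20 and 0.24 × 2 = 0.48. These are 0.20/0.57 = 0.35 and 0.48/0.57 = about 0.85 of a standard error.
- Against the implied 2.03 points, they are 10% and 24%.
- The typical (root-mean-square) shift is 0.141 × g: 0.14 points at g = 1 and 0.28 at g = 2.

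**5. Error rates.** Averaged over all randomisations, simulation gives type I error of 5.0% at g = 1 and at g = 2. Conditional on an imbalance, with p = 0.5 and total SD held at 2, the residual SD is √(4 − g²/4), or 1.94 at g = 1 and 1.73 at g = 2. Multiplying by √(2/25) gives conditional standard errors of 0.548 and 0.490. Using the 1.14 threshold and a normal approximation:

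| Case | Type I error | Power for a 2-point effect, imbalance against acupuncture |
|---|---|---|
| g = 1, 20 points | 5.1% | 88.7% |
| g = 2, 24 points | 9.0% | 78.3% |

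For g = 2 and 24 points, the upper tail is (1.137 − 0.48)/0.490 = 1.34, or about 9.0%. Power uses (1.137 − 1.52)/0.490 = −0.78, or 78%.

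**6. Gain from adjustment.** With 25 per group, a true difference of 2, p = 0.5 and total SD 2, power is 93.4% unadjusted. Adjusted, it is 94.7% at g = 1 and 97.9% at g = 2. If SD 2 instead describes variation within each timing group, the total SD is √(4 + g²/4) and unadjusted power is 91.9% or 87.3%; adjustment then recovers the 93.4%. Either way, no extra patients are needed.

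**The case against.** The strongest reply is that randomisation already deals with this. Variation due to timing is part of the SD that the t-test uses, the overall type I error is unaffected, and the shifts computed above are all below one standard error. That stands. A reader might infer from the open entry criterion that the comparison is biased or the test invalid; the documents do not support that.

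The size rests on assumptions, and that stands too. Section C(i) gives no BPI-SF trajectory and no nine-week change. It describes recent cases as both worsening and improving, and these courses could partly cancel. Neither the sign nor the size of g is known. A 2-point gap would equal the whole implied treatment effect and explain 25% of outcome variance (1/4 × 2² ÷ 2²), which is a generous upper case.

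Three further inferences are tempting and go beyond the text:
- That time since chemotherapy is the strongest predictor. The background ranks none, and it also ties neuropathy to cumulative dose.
- That allocation is simple randomisation. The method is not described, and Figure 1 might show a restriction.
- That 6 months is a prognostic cut. In the background it is only the time point of a persistence figure.

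It can also be said that the planned one-way ANOVA, or the patient characteristic datasheets in section E(i), might include time since chemotherapy. They might, but neither would adjust the comparison between arms. Finally, broad entry fits the stated purpose; nothing here requires narrowing it.

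**Conclusion.** The point holds as an optional improvement, not a validity error. The plan admits patients at any time after chemotherapy, its background makes that time plausibly prognostic, and neither the readable allocation text nor the arm comparison uses it.

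If half the patients are recent cases and allocation is unrestricted, about one trial in five would have an imbalance of 20 points or more. With an assumed gap of 1 to 2 points, an imbalance of 20 to 24 points moves the estimate by 0.2 to 0.5 points, which is noticeable beside an implied effect of about 2 but smaller than the standard error of 0.57. The expected gain from adjustment runs from slight (93% to 95% power at a 1-point gap) to useful (98% at 2 points). If the factor proves weakly prognostic, little is gained.

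**What to change.** - Record the date of the last neurotoxic dose on the baseline characteristic datasheet already planned in section E(i).
- Replace the two-sample t-test for the arm comparison with a linear model (ANCOVA) that contains treatment, baseline score and time since last dose, prespecified before the data are seen.
- If randomisation has not started, also use permuted blocks stratified by a prespecified two-level split of that time, and include the stratum in the model. Six months is one possible split; it is a reviewer's choice, not a cut the plan establishes.
- Show the effect by stratum descriptively, so that a reader can see whether it lies in recent or persistent neuropathy. The trial is too small to test a difference between strata.
- If randomisation has started, the prespecified covariate alone still recovers the precision and corrects for imbalance.

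Cost: one date field, a slightly more complex allocation list and one model degree of freedom for the timing term. No extra patients or visits, and no change to who is eligible.

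### The second blood sample is tied to finishing all 15 sessions rather than to the week-9 assessment, so patients who miss or stop sessions but stay in follow-up have no planned second sample (minor)

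*Combined protocol and SAP*

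**What the plan says.** All the relevant text is in the combined protocol and SAP, section D.

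- Blood sampling, D(i): "15 cc of blood samples will be drawn before and after 15 sessions of treatments from participants in both groups". TNF-alpha, IL-6, IL-10 and BDNF are then measured "to evaluate the differences in the inflammation state of the peripheral nervous system within and between groups".
- Course of treatment, D(i): "Acupuncture treatment will be performed for 9 weeks", given "twice a week for the first six weeks, and once a week for the following three weeks". This frequency appears under the acupuncture group only. The blood-sampling sentence applies the 15 sessions to both groups.
- Questionnaires, D(i): "questionnaires were assessed before treatment, at week three, week six, and week nine".
- Expected losses, D(ii): for acupuncture, "The treatment group often withdrew from the trial due to frequently acupuncture or bleeding caused by acupuncture"; for control, "The control group may not be able to continue treatment due to low efficacy". The remedies offered are consent-form wording and subject allowances.

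The text does not say whether or when a patient with fewer than 15 sessions is sampled. It gives no rate of non-completion, and no analysis set or missing-data rule for the markers or any other outcome. The flow chart in D(i) is not reproduced in the text available for review.

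**The concern.** The plan runs on two clocks. Symptom scores are collected by calendar week, and the second blood sample by session count. For a patient exactly on schedule the two coincide. For anyone else they separate: a patient who makes up a missed session late is bled after the week-9 questionnaire, and a patient who ends on 14 sessions never meets the stated condition.

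Reaching 15 sessions is a post-randomisation event. Section D(ii) expects failure to reach it for reasons that differ by arm, and low efficacy in the control arm is a reason related to outcome. If only those who reach 15 sessions are sampled, the arms being compared are no longer the randomised arms. Samples are also lost from a trial of about 25 per arm, and some markers no longer pair with the week-9 symptom score. Unlike a gap in the analysis text, this cannot be repaired afterwards, because a sample that was not drawn cannot be analysed.

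**Working it through.** **1. The plan's own figure.** Inputs from D(i): twice weekly for six weeks, then once weekly for three. Sessions = 2 x 6 + 1 x 3 = 15, matching the 15 in the blood-sampling sentence. The trigger is the complete course, and one session missed and not made up leaves 14.

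**2. Samples at stake.** Input from D(i): 25 per arm. The plan gives no non-completion rate, so I assume 10%, 20% and 30%. Paired samples per arm = 25 x (1 - rate) = 22.5, 20 and 17.5, a loss of 2.5, 5 and 7.5. These are ceilings on what the trigger costs, since some of these patients will have left the trial and would miss a week-9 sample too.

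**3. Power.** The plan gives no effect size or SD for the markers; "The estimated standard deviation was 2" belongs to the BPI-SF calculation. Assuming a standardised marker effect of 1, a two-sided 5% t-test has power 93% with 25 per arm, falling to 91%, 87% and 82% at the three rates.

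**4. Bias in the between-arm difference, with no true effect.** Further assumptions: 25 per arm; the same non-completion rate in each arm; correlation r = 0.3 or 0.5 between marker change and symptom change; only completers sampled. Tilt is the coefficient b in the weight exp(b x score), where a higher score is a poorer response and the weight governs the chance of not completing. Results are from simulation and agree across repeat runs to about 0.01 SD in bias and 1 percentage point in type I error.

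| Control tilt | Acupuncture tilt | Bias (SD) | Type I error |
|---|---|---|---|
| 1.5 | 0 (random loss) | 0.03 to 0.19 | about 5% to 9% |
| 0.5 | 0 (random loss) | 0.01 to 0.09 | about 4% to 6% |
| 1.5 | 0.75 | 0.01 to 0.06 | about 5% to 6% |
| 1.5 | 1.5 | about 0 | about 5% to 6% |

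**5. Extreme case by formula.** Suppose exactly the worst-responding fraction p of controls is unsampled and acupuncture losses are random. Then bias = r x phi(z_p)/(1 - p), where phi is the standard normal density and z_p its p-quantile.

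- p = 0.1, r = 0.3: 0.3 x 0.195 = 0.06 SD.
- p = 0.3, r = 0.5: 0.5 x 0.497 = 0.25 SD.

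In the second case, with 30% loss in both arms, SE = sqrt(2/17.5) = 0.338 SD. The shift is 0.248/0.338 = 0.73 SE and the type I error is about 11%.

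**6. Direction.** Losing poor responders from control makes the remaining controls look better, so in steps 4 and 5 the bias favours control.

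**7. Within-arm change.** Equal tilt cancels between arms but not within them. At tilt 1.5 the completers' mean change in an arm is shifted by about 0.04 to 0.18 SD towards good response, and the plan also intends within-group comparison.

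**The case against.** The strongest reply is that 15 sessions is shorthand for the end of the course. It equals the scheduled nine weeks, so for on-schedule patients the sample falls with the last questionnaire, and the missing flow chart may place it at a visit. This is a reasonable reading of the intent. It does not settle what happens to a patient who is off schedule.

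A reader might infer that the plan excludes non-completers and so makes the marker analysis a completer analysis. The documents do not say this. They are silent on patients with fewer than 15 sessions; a completer sample is what follows if the sentence is applied literally.

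A reader might also charge every lost sample to the trigger. That is not supported either. For acupuncture, D(ii) speaks of withdrawal from the trial, and those patients would miss a week-9 sample as well. Only patients who stop or miss treatment but keep attending would be recovered. The control-arm wording, which concerns continuing treatment, allows for such patients, but their number is unknown.

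The objection that the bias depends on an assumed asymmetry also stands. D(ii) gives reasons but no rates and no link to the markers, and under equal tilt the between-arm bias vanishes. The wider absence of an analysis set and missing-data rule affects the questionnaires too and is a separate matter.

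**Conclusion.** The point holds as a minor one. The only stated condition for the second sample is completion of every planned session, while the symptom assessments run by week. Patients who fall short of 15 sessions but remain in follow-up therefore have no planned sample, or have a mistimed one.

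The effect on the between-arm marker comparison cannot be derived from the documents. On the assumptions shown it runs from about zero, when losses relate to response similarly in both arms, to about 0.2 SD when only control losses do (0.25 SD in the extreme case). The loss of samples is at most about 2 to 8 of 25 per arm at 10% to 30% non-completion, and less to the extent that those patients have left the trial.

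It would be tempting to conclude that the trigger could manufacture a mechanism finding for acupuncture. The D(ii) reasons do not support that: in the scenario they suggest, the bias favours control and would more readily hide a true effect. The markers are exploratory, and the null hypothesis and sample size rest on BPI-SF, which this point does not touch.

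**What to change.** Replace the session-count trigger with a calendar one. Suggested wording: *The second blood sample is taken at the week-9 assessment visit from every randomised patient who still attends and agrees, whatever the number of sessions completed. Markers are analysed by randomised arm among all patients sampled; an analysis restricted to patients with 15 sessions is a sensitivity analysis.* Record the number of sessions received and the date of each sample.

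The cost is a short protocol edit, with no more blood draws or assays than already planned and no change to treatment. The drawback is that some samples will come from patients with fewer than 15 sessions, which may dilute a true effect; the completer analysis shows how much this matters. I would not add a sample at withdrawal: the documents contain no withdrawal visit, and such samples would again fall away from week 9. Patients who leave the trial before week 9 will remain unsampled, so their number and reasons should be reported by arm.

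### The only between-group test ignores the baseline score, so the trial gives up precision that its own pre-treatment questionnaires could supply

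*Combined protocol and SAP*

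**What the plan says.** All of this stands in section D(i) of the combined protocol and SAP.

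- **Hypothesis:** "the null hypothesis will be no significant difference in BPI-SF between the two groups". The BPI-SF item or composite and the time point are not given.
- **Sample size:** "The estimated standard deviation was 2, the power was set to 94%, a two-tail test", with a 5% significance level and at least 25 patients per group. The difference to detect is not stated. Nor is it stated whether the SD is that of a score or of a change.
- **Between-group analysis:** "A two-sample t-test will be used to compare the difference between the treatment group and the controlled group". It is not defined as a comparison of follow-up scores or of changes from baseline.
- **Other analyses:** "A Paired-t-test will be used to compare the changes in the assessment scale at week 3, week 6 and week 12", and a one-way ANOVA relating demographics, cancer grade and other categorical variables to the scale.
- **Schedule:** "questionnaires were assessed before treatment, at week three, week six, and week nine". A baseline value is therefore planned for BPI-SF, FACT/GOG-NTX-13 and WHOQOL-BREF.
- **Allocation:** randomised, with no stratification by baseline score described.

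**The concern.** Only the two-sample t-test compares the arms. The paired t-test looks at change over time, and the one-way ANOVA does not adjust the treatment effect for the starting score. No ANCOVA, regression or mixed model appears anywhere in the document.

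With about 25 patients per arm, the groups can easily start some tenths of a point apart by chance. A comparison of follow-up scores then carries part of that gap into the treatment estimate. A comparison of change scores over-corrects and carries part of it in the opposite direction. ANCOVA has a smaller residual variance than either. At stake are the width of the confidence interval, power if the true effect is smaller than planned, and a result open to dispute if the arms differ visibly at baseline. The validity of the test is not at stake.

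**Working it through.** **Inputs from the plan:** SD 2, power 94%, two-sided 5%, 25 per arm. **Assumed:** r = 0.3, 0.5, 0.7; equal SDs at baseline and follow-up; a roughly linear relation between them. The 1.5-point effect is illustrative only.

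**1. The plan's own figure.** Unadjusted SE = 2 × √(2/25) = 0.566. The implied difference is (1.960 + 1.555) × 0.566 = 1.99 points by the normal approximation, or 2.03 with the t distribution. Conversely, a 2-point difference needs 2 × 2² × (1.960 + 1.555)² / 2² = 24.7, that is 25 per arm. So 25 per arm fits an unadjusted t-test for about 2 points. Noncentral-t power (48 df) is 93.4% at 2 points and 73.8% at 1.5.

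**2. Effect of adjustment.** The ANCOVA variance is (1 − r²) times that of a follow-up-score comparison, and (1 + r)/2 times that of a change-score comparison. Power uses the noncentral t with 47 df. The shift is the part of a 1-SE baseline imbalance that enters the unadjusted estimate.

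(a) SD 2 is the score SD and the t-test is on follow-up scores. ANCOVA SE = 0.566 × √(1 − r²); shift = r × 0.566.

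| | SE | 95% CI half-width | Power at 2 | Power at 1.5 | Shift | Chance of shift ≥ 0.5 |
|---|---|---|---|---|---|---|
| Unadjusted | 0.566 | 1.14 | 93% | 74% | see rows below | see rows below |
| ANCOVA, r = 0.3 | 0.540 | 1.09 | 95% | 78% | 0.17 | 0.3% |
| ANCOVA, r = 0.5 | 0.490 | 0.99 | 98% | 85% | 0.28 | 8% |
| ANCOVA, r = 0.7 | 0.404 | 0.81 | 99.8% | 95% | 0.40 | 21% |

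The last two columns describe the unadjusted test at that r.

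(b) SD 2 is the SD of change and the t-test is on change. Score SD = 2/√(2(1 − r)) = 1.69, 2.00, 2.58, so the baseline SE is 0.478, 0.566, 0.730. ANCOVA SE = 0.566 × √((1 + r)/2); shift = (1 − r) × baseline SE, opposite in sign to the imbalance.

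| | SE | Power at 2 | Power at 1.5 | Shift | Chance of shift ≥ 0.5 |
|---|---|---|---|---|---|
| Unadjusted | 0.566 | 93% | 74% | see rows below | see rows below |
| ANCOVA, r = 0.3 | 0.456 | 99% | 90% | 0.33 | 14% |
| ANCOVA, r = 0.5 | 0.490 | 98% | 85% | 0.28 | 8% |
| ANCOVA, r = 0.7 | 0.522 | 96% | 80% | 0.22 | 2% |

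(c) SD 2 is the score SD but the t-test is on change. Unadjusted SE = 0.566 × √(2(1 − r)) = 0.669, 0.566, 0.438, giving power of 83%, 93% and 99% at 2 points. The ANCOVA figures are those in (a).

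**3. Simulation of (a)** at 2 points (20,000 trials): t-test power 93.1–93.6%; ANCOVA power 94.7%, 97.6% and 99.8%, with SEs of 0.545, 0.493 and 0.409. These SEs are about 1% above the formula because the slope is estimated.

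**4. Type I error given an imbalance.** If the arms differ at baseline by 1.96 SE, the nominal 5% test rejects a true null with probability 7.9%, 12.9%, 20.5% on follow-up scores, or 16.0%, 12.9%, 9.8% on change scores (r = 0.3, 0.5, 0.7; normal approximation). Averaged over randomisations the rate is 5%.

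**The case against.** The strongest reply is that nothing is broken. A t-test after randomisation is an acceptable primary analysis, and at the implied 2 points power only moves from 93% to between 95% and 99.8% in case (a). The larger gains are quoted at 1.5 points, which is not in the plan. The size rests on r, which is also not in the plan. At r = 0.2 the SE in case (a) would fall only from 0.566 to 0.554, or about 0.560 after allowing for the estimated slope. Eligibility is set on neuropathy grade with no minimum pain score, so a strong or linear baseline relation for BPI-SF cannot be presumed.

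Much of this stands. It makes the point a recommendation and not a fault in validity. Three qualifications follow:

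- The shift from chance imbalance is already part of the unadjusted SE. It is the same loss seen conditionally, not a second one.
- ANCOVA removes the shift only so far as the baseline relation is roughly linear.
- The 93% holds only if SD 2 describes the variable that is tested, as case (c) shows.

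Reading the t-test as one on change does not answer the point. ANCOVA variance is then still 35% to 15% lower for r = 0.3 to 0.7, and the imbalance still carries over with opposite sign.

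Nor does high planned power settle it. Section D(ii) expects withdrawals in both arms, but no allowance is stated. If 20 per arm remained (an assumption; case (a), 2 points), unadjusted power would be 87%, against 90%, 94% and 99% with ANCOVA.

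**Conclusion.** The concern holds. The single between-group test leaves out a baseline measurement that the trial already collects. The test is valid and unbiased on average; the cost is a wider interval and sensitivity to chance imbalance. For r between 0.3 and 0.7, adjustment cuts the variance by 9% to 51% against a follow-up-score test, or by 35% to 15% against a change-score test. The power gain is small at the back-solved 2 points, if SD 2 describes the tested variable, and larger for smaller effects or after dropout. That the covariate is absent is certain from the text. The size of the benefit depends on r, the difference to detect and the meaning of SD 2, none of which the documents give. This is an improvement that should be made, not a condition for the trial's validity.

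**What to change.** Make the between-group analysis of BPI-SF an ANCOVA of the follow-up score on treatment group, with the baseline score of the same scale as covariate, or the equivalent repeated-measures model over weeks 3, 6 and 9. Use the same model for FACT/GOG-NTX-13 and WHOQOL-BREF. Report the adjusted difference with its 95% confidence interval, and keep the two-sample t-test as a sensitivity analysis.

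The model needs three things that the plan leaves open:

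- the primary time point: week 9 is the last scheduled assessment, and the week 12 in the paired-test line must be reconciled with it;
- whether SD 2 is for the score or the change;
- the difference to detect.

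The blood markers, which are drawn before and after treatment, could be analysed in the same way. The Touch Test has no stated schedule, so the model applies there only if a baseline measurement is planned.

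The cost is one degree of freedom, with no new data, visits or patients. It is more than a wording change, because the investigators must commit to a primary time point. This should be settled before outcome data are unblinded.
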